## Liver function parameters

Liver function parameters of interest are total bilirubin (TBL), Alanine Aminotransferase (ALT), Aspartate Aminotransferase (AST) and alkaline phosphatase (ALP). The number (%) of participants with worst post-baseline values will be summarized:

The following summaries will be produced:

- ALT or AST > 3xULN
- ALT or AST > 5xULN
  - TBL > 2xULN
  - ALT or AST > 3xULN & TBL > 2xULN
  - ALT or AST > 3xULN & TBL > 2xULN & ALP < 2xULN

Of note, combined elevations (i.e. last 2 categories) are based on the peak values at any post-baseline time for a participant and thus do not need to be concurrent.

Liver function parameters will be listed, and periods of assessment (screening, on-treatment, short term and long term follow-up) will be flagged.

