### 3 Study design

This is a multicenter, open-label, single-arm study to evaluate the safety and dosimetry of Lutathera in adolescent patients 12 to <18 years old with somatostatin receptor positive GEP-NETs and PPGLs. The study will enroll at least 8 adolescent patients across GEP-NETs and PPGLs, including a minimum of 3 adolescents with GEP-NETs .

The study schedule for each patient consists of the screening period (up to 2 weeks) followed by the treatment period (4 treatment administrations at 8-week interval), and the follow-up period (5 years).

During the screening period of up to 2 weeks, patient eligibility will be determined according to the protocol's pre-defined inclusion and exclusion criteria. All screening assessments should be performed according to [Table 8-2](#).

Patients who meet all eligibility criteria at screening can be enrolled in the study. The enrollment and Lutathera order must be performed immediately after all eligibility criteria are verified and the patient is confirmed to be eligible.

There will be no study visits after screening and before the 1st Lutathera administration. Somatostatin receptor imaging (SRI) performed before the screening (within 3 months prior to enrollment) can be used for the assessment of patient eligibility. Laboratory tests completed before the screening can be used for the assessment of patient eligibility if performed within 2 weeks prior to enrollment.

The treatment period will consist of 4 Lutathera treatments administered at 8-week intervals. Lutathera administration will occur on Week 1 Day 1 of each cycle. Each patient will receive a total of 4 doses of Lutathera (7.4 GBq/200 mCi x 4 administrations every 8 weeks; cumulative dose: 29.6 GBq/800 mCi).

[figure not shown]
An infusion of sterile 2.5% Lysine - Arginine amino acid (AA) solution will be co-administered with each Lutathera dose for renal protection according to the approved Lutathera local prescribing information. An antiemetic will be administered for prevention of infusion-related nausea and vomiting ([Section 6.1.2](#)).

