**Figure 3-1. Study design**

In order to minimize risk for each study subject, an accelerated analysis of dosimetry and safety data will be performed for each patient in the study, to enable the Investigator to take a decision for the subsequent Lutathera doses. The results of dosimetry assessments (imaging and blood dosimetry) will be provided to the investigators for their evaluation prior to administration of subsequent therapeutic cycles in each patient. See [Section 6.5.1](#) for further information on the criteria for evaluating the need for dose modification based on safety and dosimetry data.

A total follow-up period of 5 years (60 months) after the last Lutathera dose will take place for each patient who received at least one dose of Lutathera. This follow-up period will be comprised of a short-term follow-up of 6 months to evaluate cumulative Lutathera toxicities, followed by a long-term follow up of another 54 months.

An external Data and Safety Monitoring Board (DSMB) will also operate in the study to evaluate accumulating safety and dosimetry data, to ensure the safety of adolescents enrolled in the study, and to provide recommendations to investigators as well as to the clinical team in charge of conducting the study (see [Section 10.2.1](#)).

Interim analyses was added to evaluate dosimetry and safety when at least five patients (including at least two GEP-NET patients) have completed at least one cycle of treatment. This analysis is introduced due to the slower than expected recruitment rate, and proportionally higher than expected recruitment of PPGL patients. The interim analysis would permit an evaluation across the indication in order to confirm modelling assumptions of similar dosimetry between adolescents and adults. The data from all completed treatment cycles will be presented. Analysis will be presented across both indications, as well as for GEP-NET and PPGL separately.

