Any suspected transmission via a medicinal product of an infectious agent is also considered a serious adverse reaction.

All reports of intentional misuse and abuse of the product are also considered serious adverse event irrespective if a clinical event has occurred.

Treatment-emergent elevations in AST or ALT ( $> 3 \times \text{ULN}$ ) in combination with total bilirubin  $> 2 \times \text{ULN}$  or jaundice in the absence of cholestasis (defined as ALP  $< 2 \times \text{ULN}$ ) or other causes of hyperbilirubinemia can be an indicator of severe drug induced liver injury (Hy's Law). The Hy's Law criteria may be changed to increases of transaminases 2-fold above baseline values for subjects with elevated baseline values. For this reason, a potential Hy's Law case requires expedited reporting, and will be handled as a serious unexpected adverse event

(assessing it as medically significant in the absence of any other seriousness criteria). It must be reported as an SAE to the sponsor promptly (i.e., even before all other possible causes of liver injury have been excluded). Reporting should include all available information, especially that needed for evaluating the diagnosis, severity and likelihood that the study treatment caused the reaction. For patient monitoring and to better understand potential etiologies, the investigator must initiate a close follow-up until complete resolution of the problem and completion of all attempts to obtain supplementary data.

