### **Baseline**

For safety and efficacy evaluations, the last available assessment on or before the date of first administration of study treatment is defined as the “baseline” assessment.

If patients have no value as defined above, the baseline result will be missing.

Final

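### The last liver row tests peak ALP against an upper limit, so an ALP of 2xULN or more at any other post-baseline assessment removes a participant who met all three criteria together

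*SAP*

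**What the plan says.** SAP 2.6.4, under Liver function parameters, names bilirubin (TBL), ALT, AST and ALP as the parameters of interest. "The number (%) of participants with worst post-baseline values will be summarized", it says, and five categories follow. The fourth combines ALT or AST above 3xULN with TBL above 2xULN. The fifth adds an ALP condition: "ALT or AST > 3xULN & TBL > 2xULN & ALP < 2xULN".

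A note on the last two categories says that they "are based on the peak values at any post-baseline time for a participant and thus do not need to be concurrent". It makes no separate provision for ALP. Liver parameters are also listed, with the period of each assessment flagged.

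The general text of SAP 2.6.4 plans on-treatment laboratory summaries, up to 56 days after the last dose, and separate cumulative summaries that add short-term and long-term follow-up.

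Protocol 10.1.2 describes the same pattern as a clinical event: transaminase and bilirubin elevations in combination, in the absence of cholestasis (ALP below 2xULN) or other causes of raised bilirubin. It says this "can be an indicator of severe drug induced liver injury" (Hy's Law) and requires a potential case to be reported promptly as an SAE.

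**The concern.** Taking peaks without regard to timing is a cautious screen when a high value is what qualifies a participant. ALT/AST and TBL work that way. ALP does not: a high value disqualifies. Applied to all three analytes, the rule changes direction at the one condition that sets an upper limit. The test becomes whether ALP stayed below 2xULN at every post-baseline assessment, rather than whether cholestasis was absent when the liver enzymes and bilirubin rose.

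An unrelated ALP rise is plausible here. Participants are 12 to under 18 years old with metastatic or inoperable locally advanced disease. Total ALP is part of the chemistry panel (Protocol Table 8-4), and bone ALP is followed as a bone-development marker (Protocol Table 8-5). Chemistry continues every six months in long-term follow-up (Protocol 4.3).

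At stake is whether the table agrees with the SAE data. A case reported as an SAE under Protocol 10.1.2 could be missing from the row built on the same three thresholds.

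**Working it through.** The plan states no expected count for these rows and no total window, so there is no planned figure to reproduce. The check has three parts.

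**1. Direction of the rule.** Write each value as a multiple of ULN. Under the SAP note, the fifth category is:

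max(ALT or AST) > 3, and max(TBL) > 2, and max(ALP) < 2, each maximum taken over all post-baseline assessments.

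- max(x) > c holds if any one value exceeds c. More assessments can only make it true.
- max(ALP) < 2 holds only if every value is below 2. More assessments can only make it false.

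**2. Constructed participants.** Each has 26 post-baseline assessments. Unless stated, values are ALT 1, TBL 0.8 and ALP 1.1 (ALP 1.2 in the altered visits of C). The same-assessment rule asks whether any single assessment meets all three conditions.

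| Participant | Fourth category | Fifth category, SAP peak rule | Same-assessment rule |
|---|---|---|---|
| A: ALT 6, TBL 3, ALP 1.2 at one visit; ALP 2.3 at a much later visit | counted | **not counted** | counted |
| B: as A, but the later ALP is 1.7 | counted | counted | counted |
| C: ALT 4 early, TBL 2.5 at an unrelated late visit, ALP always below 2 | counted | counted | not counted |

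A shows the loss. B shows that the later ALP must reach 2xULN; a smaller rise changes nothing. C shows the intended over-inclusion from peak ALT and TBL. As the row can err both ways, it is neither an upper nor a lower bound on the same-assessment count.

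**3. Length of the window.** Inputs:

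- Start: after baseline, which is "the last available assessment on or before the date of first administration of study treatment" (SAP 2.1.1, Baseline).
- Dosing: "The treatment period will consist of 4 Lutathera treatments administered at 8-week intervals" (Protocol 3). Four doses make three intervals: 3 x 8 = 24 weeks from first to last dose.
- Follow-up: "A total follow-up period of 5 years (60 months) after the last Lutathera dose will take place for each patient" (Protocol 3), made up of 6 + 54 = 60 months.

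Planned window = 24 x 7 / 365.25 + 5 = 0.46 + 5 = 5.46 years.

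Variations:

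- One extra week at each of the three intervals: 27 x 7 / 365.25 + 5 = 5.52 years. Adding the one-month long-term visit allowance: 5.52 + 0.08 = 5.60 years.
- One interval extended to 16 weeks (Protocol 6.5.1.1): 32 x 7 / 365.25 + 5 = 5.61 years. All three extended: 48 x 7 / 365.25 + 5 = 5.92 years.
- On-treatment version: 24 + 8 = 32 weeks, or 0.61 years.

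The full window exists only at the final analysis. The interim and primary analyses cut the data earlier.

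**Effect of one participant.** Protocol Amendment 03 records 11 patients enrolled. One participant of type A turns 1/11 = 9.1% into 0/11 = 0%.

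**The case against.** The strongest reply is that nobody is lost. The fourth category has no ALP condition and uses the same inclusive peaks, so every genuine case is counted there. Liver values are listed by period, all laboratory data are listed, and potential Hy's Law cases are to be reported as SAEs, which SAP 2.6.1 tabulates on treatment and lists in follow-up. With about 11 participants, the fourth category can be checked against the listing by eye. All of this stands, and it limits the harm. It does not make the fifth row right. The ALP condition is all that separates the fifth row from the fourth, and it is the condition that fails.

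A second reply is that the SAP note speaks of elevations, and ALP below 2xULN is not one, so ALP may not have been meant. But the note names the last two categories without exception. If ALP was meant to be exempt, the SAP does not say which ALP value to use, and the same sentence is needed.

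Third, Protocol 10.1.2 does not require a single sample. That is correct. It does, however, describe a combined event without cholestasis, not an ALP that stays low through follow-up.

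A reader might infer that this row decides whether a drug-induced liver injury occurred. Neither document says so. The SAP offers five descriptive counts, and the protocol places identification with SAE reporting by the investigator.

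**Conclusion.** The rule as written runs the wrong way for ALP. It can leave a participant who met all three criteria at one assessment out of the last liver row. The consequence is a possible undercount in one descriptive row, which may then disagree with the SAE data. It is not a missed case in the report as a whole. It deserves correction because the study is small enough for one participant to decide whether the row reads zero.

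The conclusion rests on reading the note as covering ALP, which is its plain meaning. The exposure is greatest at the final analysis, with a planned window of about 5.5 years.

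A reader might also want a probability that a genuine case is dropped. The documents do not support one. They give no rate of ALP at or above 2xULN, and the number of chemistry panels cannot be counted from the text available because the chemistry row of the assessment schedule (Protocol Table 8-2) is not in it. Independence between visits would also be doubtful, since ALP raised by growth or disease tends to persist. Where ALP is also high at the liver event, a same-sample rule excludes the participant too.

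**What to change.** In SAP 2.6.4, Liver function parameters:

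- For the last category only, take ALP from the same sample as the qualifying ALT/AST and TBL elevation, or from the closest sample within a stated window. If the two peaks are not concurrent, state which elevation anchors ALP.
- Keep the peak rule for ALT/AST and TBL, and keep the fourth category unchanged as the sensitive screen.
- List each participant with ALT/AST above 3xULN and TBL above 2xULN, with the dates and the ALP at that time.

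The cost is one sentence in the SAP, one derived flag and a short listing drawn from data already collected. No threshold, visit or sample changes.

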## 2.6.5 Other safety data

### 2.6.5.1 ECG and cardiac imaging data

12-lead ECGs including PR, QRS, QT, QTcF, and RR intervals will be obtained for each participant during the study. ECGs are reviewed locally by each investigative site and assessed centrally.

The summaries will include all on-treatment assessments available no later than 56 days after the last study treatment administration date (see Section 2.1.1).

The following summaries will be presented:

- Change from baseline for ECG parameters by timepoint.
- Number and percentage of patients with on-treatment notable ECG values.
  - QT or QTcF
    - New value of > 450 and ≤ 480 ms
    - New value of > 480 and ≤ 500 ms
    - New value of > 500 ms
    - Increase from baseline of > 30 ms to ≤ 60 ms
    - Increase from baseline of > 60 ms
  - HR (=60/RR in seconds)
    - Increase from baseline >25% and to a new HR > 100 bpm
    - Decrease from baseline >25% and to a new HR < 50 bpm
  - PR
    - Increase from baseline >25% and to a new PR > 200 ms
    - New PR > 200 ms
  - QRS
    - Increase from baseline >25% and to a new QRS > 120 ms
    - New QRS > 120 ms

ECG parameters will be listed, and periods of assessment will be flagged.

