## 8 Visit schedule and assessments

Participants should be seen for all visits/assessments as outlined in the assessment schedule ([Table 8-2](#)). All data obtained from these assessments must be supported in the participant's source documentation. Missed or rescheduled visits will not lead to automatic discontinuation.

The screening period must be shortened as much as possible in order to enroll and treat the patients shortly after the informed consent signature. As Lutathera production and shipment will take approximately 12 days, Lutathera first dose must be ordered immediately after confirming patient eligibility and enrollment. There will be no study visits after screening and before the 1st Lutathera administration.

The treatment period consists of 4 treatment cycles, with Lutathera administration on Week 1 Day 1 of each cycle. The dosimetry assessments will be performed during the first week after the 1st Lutathera dose as per [Table 8-2](#) and [Table 8-3](#). In the exceptional circumstances when dosimetry cannot be done in a particular patient after the first dose, it should be done as soon as feasible upon a later dose. Patients might need to stay overnight at the hospital or another facility for the days with intensive assessments (e.g. for Lutathera administration, blood sampling and imaging). The decision on the overnight stay is up to Investigator, as appropriate according to medical judgment, local regulation and patient's preference.

The End of Treatment (EoT) visit should be performed in 8 weeks after the last Lutathera administration for patients who complete all 4 Lutathera doses (end of Cycle 4). Participants who prematurely discontinue the study treatment for any reason should be scheduled for the EoT/Early Termination visit as soon as possible, at which time all of the assessments listed for the EoT visit will be performed (refer to "*EoT or early termination*" column in [Table 8-2](#)). At this EoT visit, all adverse events and concomitant medications taken during the Treatment period should be reconciled and recorded on the eCRF.

During the short-term follow-up, visits will occur every 6 weeks until 6 months after the last Lutathera dose, and during the long-term follow-up visit will occur every 6 months until 5 years after the last Lutathera dose. The last follow-up visit (5 years after the last dose of Lutathera) will be considered as End of Study (EoS) visit for each patient.

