|                       |                  | 12. Blood collection for dosimetry includes 6 radioactive blood samples at the following time points: before the start of Lutathera infusion, at the end of Lutathera infusion, then at 2h, 6h, 24h and 72h after the end of Lutathera infusion.
13. On Day 1 of Cycle 1, safety biomarkers are assessed pre-dose.
14. Safety biomarkers are taken either at Week 7 of cycle 1 or pre-dose of cycle 2.
15. Safety Biomarkers are taken either at Week 7 of cycle 4 or at the EoT visit.
S = assessment to be recorded in the source documentation only and not recorded in CRF page.
* The last FU visit would be the EOS visit for patients who completed the long-term FU period; and a separate EOS visit should be planned for patients who discontinued from the study prior to completion of the long-term FU period. |                |               |         |               |         |         |            |         |         |  |                          |                          |                          |  |

Variations of  $\pm$  1 week are allowed for the visits during the Treatment period (including the window for Lutathera administration visits that should occur in 8 weeks from the previous dose  $\pm$  1 week), and during the Short-term Follow-up. The exception is the week when dosimetry assessments are performed – during the dosimetry week, all visits must occur on the Days specified in the [Table 8-2](#).

During the Long-term Follow-up, a visit window of  $\pm$  1 month is allowed.

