### **12.5.2 Safety endpoints**

For all safety analyses, the FAS will be used. All listings and tables will be presented for all GEP-NET and PPGL participants as a pooled cohort.

Safety summaries (tables, figures) include only data from the on-treatment period with the exception of baseline data which will also be summarized where appropriate (e.g. change from baseline summaries) and long-term safety assessments which will be summarized separately. In addition, a separate summary for death including on treatment and post treatment deaths will

be provided. In particular, summary tables for adverse events (AEs) will summarize only on-treatment events, with a start date during the on-treatment period (treatment-emergent AEs).

The on-treatment period lasts from the date of first administration of study treatment to 56 days after the date of the last actual administration of Lutathera.

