### On-treatment assessment/event and observation periods

For adverse event reporting, the overall observation period will be divided into three mutually exclusive segments:

1. **Screening period:** from day of patient's informed consent to the day before first administration of study treatment
2. **on-treatment period:** from date of first administration of study treatment to 56 days (i.e. 8 weeks) after date of last actual administration of study treatment (including start and stop date).
3. **short-term follow-up period:** from day 57 after last administration of study treatment to day 183 (6 months) after date of last administration of study treatment
4. **long-term follow-up period:** starting from day 184 after last administration of study treatment

Safety summaries (tables, figures) include data from either on-treatment, short-term and long-term follow-up periods cumulatively with the exception of selection period data or baseline data which will also be summarized where appropriate. In particular, summary tables for adverse events (AEs) will summarize only on-treatment events, with a start date during the on-treatment period (**treatment-emergent** AEs) and specific listings of related SAEs and adverse events of special interest (AESI) will be provided for the short-term and long-term follow-up periods.

However, all safety data (including those from the short-term and long-term follow-up periods) will be listed and those collected during the short-term and long-term follow-up periods will be flagged.

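### ECG summaries stop at day 56 after the last dose, the nominal day of the End of Treatment visit, so an End of Treatment ECG taken on days 57 to 63 would be listed but not tabulated

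*SAP*

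**What the plan says.** SAP 2.6.5.1 plans two ECG summaries, change from baseline by timepoint and counts of notable values, and limits both: "The summaries will include all on-treatment assessments available no later than 56 days after the last study treatment administration date". This follows the general definition in SAP 2.1.1, where the on-treatment period runs from first dose "to 56 days (i.e. 8 weeks) after date of last actual administration of study treatment (including start and stop date" and short-term follow-up runs "from day 57 after last administration of study treatment to day 183". Protocol 12.5.2 sets the same limit: "The on-treatment period lasts from the date of first administration of study treatment to 56 days after the date of the last actual administration".

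The visit schedule comes from the protocol. Section 8 says "The End of Treatment (EoT) visit should be performed in 8 weeks after the last Lutathera administration" for patients who complete four doses, and calls this the end of Cycle 4. The note under Table 8-2 says that variations of ± "1 week are allowed for the visits during the Treatment period" and during short-term follow-up. Protocol 8.4.5 schedules ECGs at screening, after each infusion procedure and at EoT, and none in follow-up.

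Laboratory data (SAP 2.6.4) and vital signs (SAP 2.6.5.2) have the same 56-day sentence, but there it goes on to provide separate cumulative summaries that take in follow-up. The ECG section has no such addition.

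**The concern.** The last day that counts as on-treatment is the same day on which the EoT visit is due, so there is no margin. A visit one day late, and still inside a one-week tolerance, moves from the treatment phase to follow-up. For ECG no follow-up table exists to receive it, so the reading is left in the listing alone.

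The reading matters more than its number suggests. Every other scheduled post-baseline ECG is taken straight after an infusion procedure. EoT is the only planned look at ECG intervals some weeks after the fourth dose. In a study of 8 to 11 patients, the EoT row of the change-from-baseline table could lose several of them, for a reason that has nothing to do with the patient or the drug. In the notable-value table the patient stays in through the post-infusion ECGs, but an abnormal EoT value would not be counted.

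**Working it through.** Days are counted from the last dose, with the dosing day as day 0.

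**1. The boundary and the visit.** The SAP equates its 56-day limit with 8 weeks, and 8 × 7 = 56 reproduces it. The EoT visit is due at 8 weeks, also day 56. The nominal visit day and the last included day coincide.

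**2. The window.** Day 56 ± 7 gives days 49 to 63, or 15 possible days. Days 49 to 56 (8 days) meet the limit. Days 57 to 63 (7 days) do not. The excluded share of the window is 7/15 = 46.7%.

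**3. Is there a rule that brings a late EoT back in?** The SAP paragraph on unscheduled visits rejects windowing for those visits and says that by-visit summaries use scheduled visit names. It does not say that a scheduled visit after day 56 stays on-treatment, and 2.6.5.1 states its own date limit.

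**4. How many patients?** The documents give no distribution of EoT dates, so the late share p is an assumption. Expected number affected = n × p; chance of at least one = 1 − (1 − p)^n. The sample size is at least 8 (Protocol 12.8), and 11 had been enrolled when Amendment 03 was written. All patients are treated as following the 8-week EoT schedule.

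| Late share p (assumed) | Expected of 8 | At least one of 8 | Expected of 11 | At least one of 11 |
|---|---|---|---|---|
| 10% | 0.8 | 57% | 1.1 | 69% |
| 25% | 2.0 | 90% | 2.75 | 96% |
| 46.7% (even spread over the window) | 3.7 | 99% | 5.1 | 99.9% |

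**5. Safety biomarkers, for comparison.** Table 8-2 says: "Safety Biomarkers are taken either at Week 7 of cycle 4 or at the EoT visit". A Week 7 sample falls on about days 42 to 48, or up to day 55 with the window, and stays on-treatment. A sample at an EoT visit on days 57 to 63 leaves the on-treatment tables, but SAP 2.6.4 repeats its worst-grade and shift tables with follow-up included, so it is still tabulated. The loss from all tables is confined to ECG.

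**The case against.** Four points can be made for the plan.

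- **The window may not apply to EoT.** Table 8-2 gives EoT its own column, and the window note names only treatment-period and short-term follow-up visits. That stands as a caution: the window is an inference, drawn from Section 8 calling EoT the end of Cycle 4. If no window applies, an EoT visit after day 56 is simply off schedule, and its ECG is still excluded by the same rule.
- **SAP 2.1.1 says that safety summaries are cumulative over the treatment and follow-up periods.** Read alone, that would keep a late ECG in. But 2.6.5.1 is the specific rule, and the SAP document history records the move to cumulative summaries for laboratory data and vital signs only. The specific reading is the stronger one; the conflict is real and needs resolving either way.
- **All ECGs are listed with the period flagged, and a listing of 8 to 11 patients can be read by eye.** True, and it limits the harm. It does not repair the tables, which are the planned summaries.
- **Day 56 is prespecified in the protocol, the analyses are descriptive, and the primary safety endpoint covers the first cycle only.** All true. No primary result is touched.

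A reader might also infer that the EoT biomarkers are lost, leaving the end-of-cycle-1 draw as the only on-treatment value after baseline. The documents do not support that as a general statement. The Week 7 option keeps a sample on-treatment, the repeated tables in 2.6.4 hold the late ones, and Protocol Table 8-1 lists biomarkers for all four cycles.

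**Conclusion.** The gap is real but narrow. Following SAP 2.6.5.1 as written, an EoT ECG on days 57 to 63 enters no ECG table, whereas one on days 49 to 56 enters both. It would be too much to say that all in-window EoT ECGs are lost, or that EoT is the only infusion-free ECG, since screening provides one as well.

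The size is about 0.8 to 3.7 of 8 patients if 10% to 47% of EoT visits are late. The upper figure assumes an even spread over the window, which nothing in the documents supports or rules out; it should not be read as an estimate. The conclusion also rests on the ±1 week window applying to EoT and on 2.6.5.1 prevailing over the general sentence in 2.1.1.

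A reader might go on to infer that the on-treatment boundary for adverse events should move to each patient's EoT date. The documents do not call for that. Protocol 12.5.2 fixes 56 days, SAP 2.4.2 (concomitant medications) and SAP 5.1.1 (end-date imputation) use the same limit, and a boundary tied to visit dates would make each patient's treatment-emergent period depend on scheduling.

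This is a cheap improvement to a descriptive secondary safety analysis, worth making before the tables are produced.

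**What to change.** - In SAP 2.6.5.1, state that the scheduled EoT ECG is included by visit name in the by-timepoint and notable-value tables, whatever its day relative to day 56. This also settles EoT visits after early discontinuation, which Protocol Section 8 asks for as soon as possible, without an upper limit in days; a fixed day-63 limit would not cover all of these.
- Reconcile 2.6.5.1 with the sentence on cumulative summaries in SAP 2.1.1, saying which governs ECG.
- Optionally, apply the same visit-name rule to EoT safety biomarkers in the on-treatment tables of SAP 2.6.4.
- Leave the 56-day on-treatment boundary for adverse events unchanged. Note the ECG exception in SAP section 4, because Protocol 12.5.2 otherwise confines safety summaries to the on-treatment period, with separate long-term summaries.

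The cost is a sentence or two and a selection rule in the ECG programs, with no new data. The downside is that a few ECGs taken somewhat more than 56 days after the last dose, or later still after early discontinuation, would be counted in the treatment-phase tables; a footnote giving the days since last dose would make this visible.
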